#### **7.10 Dispensing Study Drug**

Study drug will be dispensed to the subject in a 4-vial carton as per schedule of events.

The investigator will be responsible for the maintenance of records of receipt and disposition of study drug including dates, quantities administered and availability, and subject assignment.

#### **7.11 Treatment Compliance**

Treatment compliance will be verified by investigative sites. Subjects will be asked to return all their used and unused cartons with vials to the investigative site for accountability as per schedule of events.

Subjects that miss more than four doses of study drug over the course of the study, or miss two consecutive doses of study drug during the dose escalation phase are considered non-compliant. A subject will also be considered non-compliant if he or she is judged by the investigator to have intentionally or repeatedly taken more than the prescribed amount of study drug. Subjects that are noncompliant will be discontinued from the study (see section 5.2).

## 7.12 Concomitant Medication Assessments

Medications ongoing at the time of visit 1 as well as any new medication added during the course of the study will be recorded in the source document and eCRF as concomitant medications.

## 8 SAFETY EVALUATIONS

Investigators are responsible for monitoring the safety of subjects who have entered this trial and for alerting the sponsor or its designee of any event that seems unusual, even if this event may be considered an unanticipated benefit to the subject.

The investigator remains responsible for following through an appropriate health care option, AEs that are serious, considered related to the study treatment or the trial or that caused the subject to discontinue before completing the trial. The subject should be followed until the event is resolved or deemed to be chronic. Frequency of follow-up evaluation is at the discretion of the investigator.

In addition to records of observations made at specific times, unexpected signs and symptoms and concomitant medications will be recorded in the clinical trial records throughout the study.

### 8.1 DSMB

A sponsor-appointed medical monitor will oversee subject safety in this study. An independent data and safety monitoring board (DSMB) consisting of one statistician and three clinicians with appropriate expertise will monitor the study at regular intervals, and may make recommendations for changes to the conduct of the trial to reflect safety concerns. Specific responsibilities and activities of the DSMB will be defined in the charter to be ratified at the organizational meeting of the DSMB. The DSMB will also perform an assessment of the tolerability of the 70 mg dose level (see section 8.10.2).

### 8.2 Adverse Events

An adverse event (AE) is any untoward medical occurrence in a patient or clinical investigation subject administered a pharmaceutical product and which does not necessarily have a causal relationship with this treatment.

All subjects will be monitored, evaluated and queried for AEs at each visit. Subjects may be asked to self-report AEs verbally during visits and they will be encouraged to self-report AEs in their diaries between visits. All AEs, including SAEs occurring after the subject signs the ICF through the subject's final visit will be reported and monitored. AEs that occur following first administration of study drug are TEAEs. Any clinically significant abnormal laboratory results, physical examination findings, ECGs, and vital signs will be reported as AEs. Unless related to protocol procedures as deemed by the investigator, clinically significant findings reported prior to administration of first dose of study drug are exclusionary. All AEs will be reported to the sponsor via eCRF.

All AE/SAEs will be followed through to resolution or until the investigator assesses the AE/SAEs as resolved, chronic or irreversible. The investigator is not obliged to follow-up with subjects for AEs or SAEs that begin after study completion, however if an SAE is reported to the investigator after a subject has completed the study, and it is 'possibly related' to the study drug, then the investigator will report it to the sponsor.

### **8.2.1 Severity**

The intensity of the AE will be rated by the investigator as mild, moderate or severe using the following criteria:

- Mild: Symptoms causing no or minimal interference with usual social and functional activities
- Moderate: Symptoms causing greater than minimal interference with usual social and functional activities
- Severe: Symptoms causing inability to perform usual social and functional activities

It should be noted that the clinical severity and seriousness of an AE are not synonymous, eg, a severe headache is not classified as serious until it meets the required elements as an SAE.

The maximum severity attained for each AE reported will be recorded in the eCRFs.

### **8.2.2 Relationship**

The investigator decides whether he or she interpret the observed AEs as either related to disease, to the study medication, study procedure or other concomitant treatment or pathologies. To assess the relationship of the AE to the study drug, the following terminologies are defined:

- **Related:** the temporal sequence of the event relative to administration of the study drug is reasonable, it cannot be explained by the disease or other drugs, dechallenge (if performed) is positive and pharmacologically/pathologically plausible, rechallenge (if performed) is positive, or the event shows a pattern consistent with previous knowledge of the study drug or product class

- **Possibly related:** the temporal sequence of the event relative to administration of the study drug is reasonable, and is unlikely to be attributed to disease or other drugs, dechallenge (if performed) is positive
- **Unlikely related:** the temporal sequence of the event relative to administration of the study drug is reasonable, the event could also be explained by disease or other drugs, dechallenge (if performed) is positive or uncertain, rechallenge (if performed) is negative
- **Not related:** the temporal sequence of the event relative to administration of study drug is not reasonable, disease or other drugs provide plausible explanations, dechallenge (if performed) is negative or ambiguous

All “related”, and “possibly related” AEs and SAEs will be defined as related to study drug in this study.

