#### **8.3.2 Hypersensitivity Reactions**

All hypersensitivity reactions will be collected. Study drug should be temporarily discontinued in any individual suspected of having a severe or serious allergic/hypersensitivity reaction to study drug. Study drug may be restarted if, in the opinion of the investigator, the event was not related to study drug and when/if it is safe to do so.

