### 8.9.1 Reporting Serious Adverse Events

#### 8.9.1.1 Initial Report

All SAEs occurring from the time of informed consent until 30 days following the last administration of study drug must be reported to Medpace Clinical Safety **within 24 hours** of the knowledge of the occurrence (this refers to any AE that meets any of the aforementioned serious criteria). All known SAEs that the investigator considers related to study drug *occurring after the 30-day follow-up period* must be reported to the sponsor.

---

*Confidential*

To report the SAE, complete the SAE form electronically in the EDC system for the study. When the form is completed, Medpace Safety personnel will be notified electronically and will retrieve the form.

If the event meets serious criteria and it is not possible to access the EDC system, send an email to Medpace Safety (email address listed below) or call the Medpace SAE hotline (phone number listed below), and fax the completed paper SAE form to Medpace (fax number listed below) within 24 hours of awareness. When the EDC system becomes available, the SAE information must be entered within 24 hours of the system becoming available.

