6.11.1 Adverse Events

An AE is any untoward medical occurrence in a patient or clinical investigation subject administered a pharmaceutical product and which does not necessarily have a causal relationship with this treatment. All AEs, including SAEs, occurring after the subject signs the informed consent form (ICF) through the subject's final visit will be reported and monitored. All AEs will be coded using MedDRA version 20.1.

TEAEs are defined as events that are newly reported after first dose of study drug or reported to worsen in severity or relationship to study drug after first dose of study drug.

An overview of AEs will be provided by treatment group and in total for the following information:

- All TEAEs,
- Maximum severity of TEAEs,
- Study drug-related TEAEs (defined as related or possibly related),
- Maximum severity of drug-related TEAEs,
- All serious adverse events (SAEs),
- All treatment-emergent SAEs,

- Drug-related SAEs,
- Death due to AEs,
- Withdrawals due to AEs, and
- Withdrawals due to study drug-related AEs.

The numbers and percentages of subjects with TEAEs, including number of events, will be tabulated for each treatment group and in total by MedDRA system organ class and preferred term. Similar summaries will be provided by maximum severity. Drug-related TEAEs will be summarized in the same manner.

Listings of SAEs and AEs leading to study medication discontinuation will be provided.

Hyperglycemia

The number and percent of subjects permanently discontinued from the study due to hyperglycemia will be tabulated by treatment group for the Safety Population. The discontinuation rates will be compared among the treatment groups using a Fisher's exact test. The odds ratio will be provided.

AEs of Special Interest

The number and percent of subjects (including number of events) experiencing AESIs (GI events, major CV events, hypoglycemia, injection site reactions, hypersensitivity reactions and pancreatic events) will be tabulated for each treatment group and in total by category and preferred term. A listing will be provided of all AEs of special interest. For hypoglycemia, listings will be provided of all additional information such as glucose values, symptoms, countermeasures, etc. For injection site reactions, listings will be provided of all additional information such as symptoms, severity of each symptom, etc.

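### The causality grades in Protocol 8.2.2 overlap, and a well-timed event with a positive dechallenge can be graded *Unlikely related* and so left out of the drug-related counts

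*Protocol*

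**What the plan says.** Protocol 8.2.2 defines four grades.

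- *Related* asks for reasonable timing and no explanation by disease or other drugs, with further conditions on dechallenge and rechallenge. It ends with a clause, joined by *or*, about events that fit what is already known of the drug or its class.
- *Possibly related* asks for reasonable timing and an event that "is unlikely to be attributed to disease or other drugs, dechallenge (if performed) is positive".
- *Unlikely related* keeps the timing criterion: "Unlikely related: the temporal sequence of the event relative to administration of the study drug is reasonable". It continues: "the event could also be explained by disease or other drugs, dechallenge (if performed) is positive or uncertain". It adds that a rechallenge, where one was done, is negative.
- *Not related* requires timing that is not reasonable.

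The section closes by grouping the grades: related and possibly related "AEs and SAEs will be defined as related to study drug in this study". SAP 6.11.1 uses the same cut: "Study drug-related TEAEs (defined as related or possibly related)".

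Other provisions refer to relatedness. Protocol 5.1.2 lists SAEs and clinically significant events judged related, and drug-related systemic hypersensitivity, among the conditions for considering permanent discontinuation. Protocol 8.3.2 says: "Study drug may be restarted if, in the opinion of the investigator, the event was not related to study drug". After the 30-day window, Protocol 8.9.1.1 asks for reports of "All known SAEs that the investigator considers related to study drug". Protocol 8.2 asks for reports of possibly related SAEs that come to light after study completion.

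**The concern.** An event that either the drug or the underlying disease could have caused is the ordinary case of a possible drug effect. Here it meets the wording of the grade below, and that grade falls on the not-drug-related side of the cut. This can happen even when the event resolved on stopping the drug.

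The population makes other causes easy to find. Every subject has type 2 diabetes and a BMI of 27 to 45, and background metformin is allowed. Protocol 8.3 uses adverse events of special interest to judge tolerability. The 70 mg target is above the highest once-weekly dose described in Protocol 1.3 (60 mg).

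At stake are the summaries of drug-related TEAEs, drug-related SAEs and withdrawals for drug-related events, and the provisions listed above. If sites resolve the overlap differently, those summaries also lose consistency across up to about 30 sites.

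**Working it through.** The documents give no figure on causality grading, so there is nothing to reproduce. The check compares the grades criterion by criterion and then traces where the cut is used.

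**1. The grades side by side (Protocol 8.2.2)**

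| Grade | Timing | Other cause | Dechallenge, if done | Rechallenge, if done | Counted as drug-related |
|---|---|---|---|---|---|
| Related (main clause) | reasonable | excluded | positive | positive | yes |
| Possibly related | reasonable | unlikely | positive | not mentioned | yes |
| Unlikely related | reasonable | possible | positive or uncertain | negative | no |
| Not related | not reasonable | plausible | negative or ambiguous | not mentioned | no |

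**2. A test event.** Take an event with reasonable timing and a positive dechallenge, no rechallenge, and another cause that is possible.

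- *Related*, main clause: fails, because another cause is not excluded.
- *Related*, final clause: met if that clause stands alone and the event is a known class effect. Not met if the clause only qualifies the conditions before it. The sentence can be read either way.
- *Possibly related*: met only if the investigator thinks the other cause unlikely.
- *Unlikely related*: met on every criterion.
- *Not related*: fails on timing.

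**3. What follows**

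- If the other cause is about as plausible as the drug, and the event is not a known class effect, *Unlikely related* is the only grade that fits.
- If the other cause is possible but improbable, *Possibly related* and *Unlikely related* both fit.
- If the event is a known class effect, *Related* and *Unlikely related* may both fit.
- A well-timed event with a possible other cause and a negative dechallenge fits no grade cleanly. The scale therefore has a gap as well as overlaps.

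**4. Where the cut is used**

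| Depends on relatedness | Does not depend on it |
|---|---|
| Drug-related TEAE, SAE and withdrawal summaries (Protocol 11.4.1, SAP 6.11.1) | All-causality TEAE and AESI tables (SAP 6.11.1) |
| Related SAE or clinically significant event, and systemic hypersensitivity (Protocol 5.1.2) | Confirmed pancreatitis, nonfatal major CV events, severe injection site reactions and the discretionary item (Protocol 5.1.2) |
| SAE reporting after 30 days or after completion (Protocol 8.9.1.1, 8.2) | SAE reporting up to 30 days after the last dose (Protocol 8.9.1.1) |
| Possibly restart after hypersensitivity (Protocol 8.3.2) | DSMB tolerability rule (Protocol 8.10.2) |

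**5. Size.** Let *q* be the share of truly drug-caused events that also have a possible other cause, and suppose all of them are graded *Unlikely related*. The drug-related count then captures 1 − *q*. With *q* assumed at 10%, 30% and 50%, this gives 1 − 0.10 = 90%, 1 − 0.30 = 70% and 1 − 0.50 = 50%. These values show only how the count responds to *q*; none is an estimate for this trial.

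**The case against.** The strongest reply is that the scale is less severe than it looks.

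- **Known class effects.** Protocol 1.3 describes nausea, vomiting and diarrhea as dose-related and in line with a GLP-1 agonist effect. The final clause of *Related* may therefore capture them. This stands as one reading. It does not remove the overlap with *Unlikely related*, and it does nothing for an event not already known for the drug or class.
- **Rechallenge.** An event that recurs on re-exposure does not fit *Unlikely related*, and Protocol 5.1.1 encourages prompt restart after a temporary stop. This stands, but the condition applies only where a rechallenge took place.
- **Judgement.** A reader might infer that any nameable alternative forces an event out of the drug-related group. The text does not say so, because *Possibly related* remains open when the alternative is judged unlikely. Metformin is also a weak alternative for new symptoms, since entry requires a stable dose for at least 3 months.
- **Reach.** A reader might infer that every safety action is biased. The documents do not support that, as the right-hand column of the second table shows. In Protocol 8.3.2 it is unclear whether restart turns on the separate *Not related* grade, which an *Unlikely related* event would not meet. Restart there also depends on safety.
- **Visibility.** Protocol 11.4.1 lists every AE with its relationship, both arms are graded blind, and no between-group test of drug-related TEAEs is planned. This limits the harm but does not correct the summaries.

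**Conclusion.** The point holds as a drafting fault in a stated rule. The grades are not mutually exclusive, and the line between related and not related is in the wrong place for events with a merely possible other cause. The likely direction is an under-count of drug-related events, with inconsistent grading between investigators. The direction assumes that sites apply the written criteria and that some drug-caused events have another possible cause.

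The size is unknown. A reader might infer that most gastrointestinal events would drop out of the drug-related tables. The documents give no share on which to base that, and the final clause of *Related* may keep those events in. The efficacy analyses and the all-causality safety tables are not touched.

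**What to change.** **Preferred.** Redraft the grades in Protocol 8.2.2 to be mutually exclusive. A merely possible other cause, with reasonable timing and a dechallenge that is not negative, should not by itself remove an event from the drug-related group. State whether the final clause of *Related* stands alone, and give a place to the well-timed event with a negative dechallenge. Then reconcile Protocol 5.1.2, 8.2, 8.3.2 and 8.9.1.1 with the revised grades. Moving the cut also changes which events meet the provisions in those sections, so the sponsor's clinical team must decide how each should read. No clinical rule is proposed here.

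**If site definitions cannot change.** SAP 6.1 indicates that enrolment had already taken place, so this may be the practical route. Before unblinding, add two items to SAP 6.11.1: a table of *Unlikely related* TEAEs and SAEs by arm, and a sensitivity summary pooling them with related and possibly related events. Both need only the recorded grade. A recount based on dechallenge outcome would need data that the documents do not show are captured.

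**Cost.** The first route needs a protocol wording change, site instruction and checks on the linked sections. The second needs two added safety outputs; it repairs the reporting but not the provisions that sites act on. Either way, more events in both arms will be shown as drug-related, including some that the drug did not cause.

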### **8.3 Adverse Events of Special Interest**

The AEs of special interest (AESIs) of varying clinical significance will be used to determine the tolerability of OPK-88003 doses selected for this clinical trial. All AESIs that meet the definition of an SAE (section 8.9) must be reported as an SAE.

#### **8.3.1 Injection Site Reactions**

Injection site reactions will be collected. Assessment of severity, duration and relatedness to study drug will be recorded.

#### **8.3.2 Hypersensitivity Reactions**

All hypersensitivity reactions will be collected. Study drug should be temporarily discontinued in any individual suspected of having a severe or serious allergic/hypersensitivity reaction to study drug. Study drug may be restarted if, in the opinion of the investigator, the event was not related to study drug and when/if it is safe to do so.

#### **8.3.3 Hypoglycemia**

Fasting SMBG and central laboratory FPG values will be reviewed for hypoglycemic episodes as defined in the study manual. All episodes (documented symptomatic, asymptomatic or probable symptomatic hypoglycemia) will be recorded as an AE; those falling within AmDA classification Level 3 (see Table 3) will be recorded as an SAE. For each event, assessment of severity, duration and relatedness to study drug will be recorded.

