**Table 3 Classification of Hypoglycemia**

| Hypoglycemia Level | Glycemic Criteria             | Description  |
|--------------------|-------------------------------|--|
| Level 1            | ≤70 mg/dL (3.9 mmol/L)        | Sufficiently low for treatment with fast-acting carbohydrate and dose adjustment of glucose-lowering therapy |
| Level 2            | <54 mg/dL (3.0 mmol/L)        | Sufficiently low to indicate serious, clinically important hypoglycemia                                      |
| Level 3            | No specific glucose threshold | Hypoglycemia associated with severe cognitive impairment requiring external assistance for recovery          |

[AmDA 4 2018](#)

Subjects should be asked about symptomatic and asymptomatic hypoglycemia at each visit, and trained on treatment of hypoglycemia.

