#### **11.4.2 Adverse Events of Special Interest**

##### **11.4.2.1 Hypoglycemic Episodes**

The incidence of total hypoglycemic episodes will be presented for each visit (incidence between visits) and overall. Listings of severity of hypoglycemic episodes will be presented by visit for each subject.

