If data allows, the monthly hypoglycemia rate will be calculated as the event rate per subject year divided by 12 months:

$$(365.25 \times \text{total number of hypoglycemia TEAEs} / \text{study duration}) \div 12$$

Where study duration is the date of completion/early termination – date of first dose +1. Summary statistics for the monthly hypoglycemia rate will be provided by treatment group.

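### Apart from recording Level 3 as an SAE, no planned hypoglycemia summary or rate uses the Table 3 levels, so Level 2 is never separated from Level 1 between arms

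*Protocol*

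**What the plan says.** Table 3 of the protocol defines three levels. Level 1 is 70 mg/dL or below. Level 2 is below 54 mg/dL and is described as "Sufficiently low to indicate serious, clinically important hypoglycemia". Level 3 has no glucose threshold and rests on severe cognitive impairment that needs outside help.

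Protocol 8.3.3 sets the recording rule: "All episodes (documented symptomatic, asymptomatic or probable symptomatic hypoglycemia) will be recorded as an AE". It continues that "those falling within AmDA classification Level 3 (see Table 3) will be recorded as an SAE". On what is captured, it says: "For each event, assessment of severity, duration and relatedness to study drug will be recorded". The level is not among those items. The definition of an episode is left to a study manual.

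The only AE severity scale in the protocol is in 8.2.1, and it is functional. Its lowest grade reads "Mild: Symptoms causing no or minimal interference with usual social and functional activities".

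For analysis, Protocol 11.4.2.1 presents the incidence of total episodes, between visits and overall, and adds: "Listings of severity of hypoglycemic episodes will be presented by visit for each subject". Under SAP 6.11.1, subjects and events for the AEs of special interest, hypoglycemia among them, "will be tabulated for each treatment group and in total by category and preferred term". Glucose values, symptoms and countermeasures go into listings. If data allow, one monthly rate is calculated from the "total number of hypoglycemia TEAEs".

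**The concern.** Incidence and rate of hypoglycemia are a stated objective (Protocol 2.3, SAP 3.3). The protocol adopts a classification that separates a minor low from a clinically important one, but the planned summaries do not carry that distinction through. A pooled count shows how often episodes occur and nothing about how deep they are. Two arms could have the same count and rate while one has most of its episodes below 54 mg/dL. The tables of TEAEs by maximum severity would not reveal this, because an episode without symptoms has no functional impact to grade. A reader who wants to compare Level 2 between arms would have to work through the listings by hand, with no pre-specified rule for assigning episodes to levels.

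**Working it through.** The documents state no hypoglycemia figure to reproduce. The check is a trace of each planned output, followed by the SAP's own rate formula applied to assumed counts.

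**Step 1. Does any output separate Level 1 from Level 2?**

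| Output | Basis | Separates Level 2 from Level 1? |
|---|---|---|
| Protocol 11.4.2.1, incidence | Total episodes | No |
| Protocol 11.4.2.1, listing | Severity, per subject | No, and no arm summary |
| Protocol 11.4.1 and SAP 6.11.1, TEAEs by severity | AE severity grade | No |
| SAP 6.11.1, AEs of special interest | Category and preferred term | No |
| SAP 6.11.1, monthly rate | All hypoglycemia TEAEs | No |
| SAP 6.11.1, hypoglycemia listing | Glucose values, symptoms | Only by hand, no arm summary |
| SAP 6.11.1, SAE rows and listing | SAE status | No; isolates Level 3 only |

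**Step 2. Grading.** Take an asymptomatic reading of 45 mg/dL (an assumed example). Since 45 < 54, it is Level 2. With no symptoms there is no interference with activities, so it meets the 8.2.1 definition of mild. It also satisfies the Level 1 criterion, since 45 ≤ 70 and Level 1 has no printed lower bound. A table by level therefore needs an assignment rule.

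**Step 3. The SAP rate formula.** Monthly rate = (365.25 × events / study duration in days) ÷ 12.

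- Inputs from the documents: 70 and 40 subjects (Protocol 11.1). Follow-up is to day 239, the target day of the last visit (Protocol Appendix 1).
- Assumed: every subject is followed for 239 days. The active arm has 14 episodes, 4 at Level 1 and 10 at Level 2. Placebo has the same number per subject, 40 × 14/70 = 8, all at Level 1.
- Active, pooled: 365.25 × 14 / (70 × 239) / 12 = 0.0255 per subject-month.
- Placebo, pooled: 365.25 × 8 / (40 × 239) / 12 = 0.0255.
- Level 2 only: active 365.25 × 10 / (70 × 239) / 12 = 0.0182; placebo 0.

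The planned rate is identical in the two arms. A rate by level is not. With equal follow-up, the mean of per-subject rates gives the same result as pooling events over arm time.

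**Step 4. Dilution.** Suppose placebo has r Level 1 events for each event at Level 2 or above, and the drug triples the latter without changing the former. The pooled rate ratio is then (r + 3)/(r + 1):

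- r = 5: 8/6 = 1.33
- r = 10: 13/11 = 1.18
- r = 20: 23/21 = 1.10

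The ratio at Level 2 or above is 3 in each case. The values of r and the tripling are assumptions; neither is in the documents.

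**The case against.** The strongest reply is that the plan does not ignore the levels. Level 3 episodes become SAEs, so they reach the SAE counts by arm and the SAE listing. A severe episode also appears as a clinically significant event in Protocol Appendix 2. This stands. A reader might infer that Table 3 plays no part in any output, or that an excess of Level 3 events would be lost in the pooled count. The documents do not support either inference, and the gap concerns Level 2 against Level 1.

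Few events are also likely. Protocol 1.3 reports no evidence of a hypoglycemia-promoting effect, and metformin is the only glucose-lowering background drug allowed (Protocol 6.9). The SAP makes even the pooled rate conditional on the data. This limits what a table by level can show. It does not justify leaving the distinction to listings.

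The objective promises incidence and rate without a breakdown by level, so strictly it is met. That is also correct: this is an improvement to the summary, and no stated commitment is broken.

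That the severity assessment in 8.3.3 means the 8.2.1 scale is a fair reading, since no other scale is defined, but neither 8.3.3 nor 11.4.2.1 says so. The study manual and the table mock-ups were not available and could settle it. Protocol 8.2.1 itself notes that severity and seriousness differ, so a functional grade of mild does not contradict a biochemical Level 2. The two measure different things, and the grade need not be replaced.

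Finally, a reader might add urgency by saying that 70 mg is beyond anything tested. Protocol 1.3 and 1.4.1 limit that. It exceeds the earlier once-weekly maximum of 60 mg, but one study gave 40 mg daily for 7 days and reached exposures about three times those modelled here.

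**Conclusion.** The point holds in a limited form. Outside the SAE route for Level 3, no planned count, rate or table uses the Table 3 levels, and Level 2 is not distinguished from Level 1 in any comparison between arms. An asymptomatic Level 2 episode can be graded mild, provided the severity assessment uses the 8.2.1 scale.

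The effect on this trial's results cannot be sized from the documents. The pooled ratios of 1.10 to 1.33 against 3, and the equal rates of 0.0255 with Level 2 rates of 0.0182 and 0, show only what pooling can hide under assumed mixes. They are not predictions. The primary analysis is unaffected. This is a low-cost improvement to a stated safety objective and worth making.

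**What to change.** In SAP 6.11.1, add a derived level for each hypoglycemic episode:

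- Assign the highest Table 3 level met, using the lowest glucose value of the episode for Levels 1 and 2 and the SAE record for Level 3. This resolves the overlap of the two glucose thresholds without editing Table 3.
- Put symptomatic episodes that have no glucose value, and are not Level 3, in a separate class.
- Report subjects, events and, if data allow, the monthly rate by arm for each level and for Level 2 or above combined. Keep the total.
- State which scale the hypoglycemia severity listing refers to, and leave the 8.2.1 grade in place.

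The cost is a derivation rule and one table. No new data are needed: Protocol 7.5 has subjects record the glucose value and symptoms, and the SAP already lists both. The drawback is that counts at Level 2 or above will probably be small and their intervals wide, so the table should be presented as descriptive.
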